2.3.2 KNOWN POTENTIAL BENEFITS

2.3.2.1: CABOZANTINIB:

A phase II randomized discontinuation trial assessed cabozantinib (XL184), an orally bioavailable inhibitor of tyrosine kinases including VEGF receptors, MET, and AXL, in a cohort of subjects with metastatic melanoma. Subjects received cabozantinib 100 mg daily during a 12-week lead-in. Subjects with stable disease (SD) per Response Evaluation Criteria in Solid Tumors (RECIST) at week 12 were randomized to cabozantinib or placebo. Primary endpoints were objective response rate (ORR) at week 12 and post randomization progression-free survival (PFS). Seventy-seven patients were enrolled (62% cutaneous, 30% uveal, and 8% mucosal). At week 12, the ORR was 5%; 39% of patients had SD. During the lead-in phase, reduction in target lesions from baseline was seen in 55% of evaluable patients overall and in 59% of evaluable subjects with uveal melanoma. Median PFS after randomization was 4.1 months with cabozantinib and 2.8 months with placebo (hazard ratio of 0.59; $P=0.284$). Median PFS from study day 1 was 3.8 months, 6-month PFS was 33%, and median overall survival was 9.4 months. The most common grade 3/4 adverse events were fatigue (14%), hypertension (10%), and abdominal pain (8%). One treatment-related death was reported from peritonitis due to diverticular perforation. The rest of reported studies are detailed in Section 2.2.2.

2.3.2.2: PEMBROLIZUMAB

The safety and efficacy of pembrolizumab were evaluated in Study KEYNOTE-006 (NCT01866319), a randomized (1:1:1), open-label, multicenter, active-controlled trial. Subjects were randomized to receive pembrolizumab at a dose of 10 mg/kg every 2 weeks or 10mg/kg every 3 weeks as an intravenous infusion until disease progression or unacceptable toxicity or to ipilimumab 3 mg/kg every 3 weeks as an intravenous infusion for 4 doses unless discontinued earlier for disease progression or unacceptable toxicity. Subjects with disease progression could receive additional doses of treatment unless disease progression was symptomatic, was rapidly progressive, required urgent intervention, occurred with a decline in performance status, or was confirmed at 4 to 6 weeks with repeat imaging.

Randomization was stratified by line of therapy (0 vs. 1), ECOG PS (0 vs. 1), and PD-L1 expression ($\geq 1\%$ of tumor cells [positive] vs. $< 1\%$ of tumor cells [negative]) according to an investigational use only (IUO) assay. Key eligibility criteria were unresectable or metastatic melanoma; no prior ipilimumab; and no more than one prior systemic treatment for metastatic melanoma. Subjects with BRAF V600E mutation-positive melanoma were not required to have received prior BRAF inhibitor therapy. Patients with autoimmune disease; a medical condition that required immunosuppression; previous severe hypersensitivity to other monoclonal antibodies; and HIV, hepatitis B or hepatitis C infection, were ineligible.

Assessment of tumor status was performed at 12 weeks, then every 6 weeks through Week 48, followed by every 12 weeks thereafter. The major efficacy outcome measures were overall survival (OS) and progression-free survival (PFS; as assessed by blinded independent

central review (BICR) using Response Evaluation Criteria in Solid Tumors [RECIST v1.1]). Additional efficacy outcome measures were overall response rate (ORR) and response duration. A total of 834 patients were randomized: 277 patients to the pembrolizumab 10 mg/kg every 3 weeks arm, 279 to the pembrolizumab 10 mg/kg every 2 weeks arm, and 278 to the ipilimumab arm. The study population characteristics were: median age of 62 years (range: 18 to 89 years), 60% male, 98% White, 66% had no prior systemic therapy for metastatic disease, 69% ECOG PS of 0, 80% had PD-L1 positive melanoma, 18% had PD-L1 negative melanoma, and 2% had unknown PD-L1 status using the IUO assay, 65% had M1c stage disease, 68% with normal LDH, 36% with reported BRAF mutation-positive melanoma, and 9% with a history of brain metastases. Among patients with BRAF mutation-positive melanoma, 139 (46%) were previously treated with a BRAF inhibitor. The study demonstrated statistically significant improvements in OS and PFS for patients randomized to pembrolizumab as compared to ipilimumab.

Among the 91 subjects randomized to pembrolizumab 10 mg/kg every 3 weeks with an objective response, response durations ranged from 1.4+ to 8.1+ months. Among the 94 patients randomized to pembrolizumab 10 mg/kg every 2 weeks with an objective response, response durations ranged from 1.4+ to 8.2 months.

3 OBJECTIVES AND ENDPOINTS

OBJECTIVES	ENDPOINTS	JUSTIFICATION FOR ENDPOINTS
Primary		

Phase 1: To determine the recommended phase 2 dose (RP2D) of cabozantinib when administered orally in combination with intravenous pembrolizumab, in subjects with treatment naive advanced melanoma.
 
Phase 2: To assess the preliminary efficacy of the established dose of cabozantinib in combination with pembrolizumab in subjects with treatment naive advanced melanoma.
	
Phase 1: Incidence of dose limiting toxicities.
 
Phase 2: Best overall response rate (ORR) (complete response (CR) + partial response (PR)) per RECIST v1.1 with the established dose of cabozantinib in combination with pembrolizumab in subjects with advanced melanoma.
	
Phase 1: The combination of cabozantinib and pembrolizumab has not been tested in advanced melanoma. Therefore, the safety of this combination needs evaluation.
 
Phase 2: The best overall response rate is a suitable endpoint for the initial phase 2 study.

Secondary		

Phase 1: To assess and describe the safety profile of the combination of cabozantinib and pembrolizumab.
 
To assess and describe preliminary evidence of antitumor activity for cabozantinib in combination with pembrolizumab, in subjects with treatment naive advanced melanoma.
 
Phase 2: To evaluate time to response from the combination of cabozantinib and pembrolizumab in subjects
	
Phase 1: To describe the safety profile of the combination of cabozantinib and pembrolizumab in subjects with advanced melanoma.
 
ORR per RECIST v1.1 with the combination of cabozantinib and pembrolizumab in advanced melanoma.
 
Time to response per RECIST v1.1.
 
Phase 2: Best overall response rate (ORR) (complete response (CR) + partial
	

OBJECTIVES	ENDPOINTS	JUSTIFICATION FOR ENDPOINTS
with treatment naïve advanced melanoma. To evaluate the disease control rate (DCR) with the combination of cabozantinib and pembrolizumab in subjects with treatment naïve advanced melanoma. To evaluate the progression-free survival from the combination of cabozantinib and pembrolizumab in subjects with treatment naïve advanced melanoma. To evaluate the overall survival with the combination cabozantinib and pembrolizumab in subjects with treatment naïve advanced melanoma.	response (PR) per RECIST v1.1 criteria. Time to response per RECIST v1.1 criteria. DCR defined as the percentage of patients achieving CR + PR + SD at any time during the study following initiation of therapy. Radiologic progression-free survival (PFS) per RECIST v1.1 criteria. PFS is defined as the time between the first dose of study therapy and the earliest date of progression or death. Subjects who have neither progressed nor died will be censored at the last tumor assessment date for PFS. Overall survival defined as the time between the first dose of study therapy and death (subjects who have not died will be censored at the most recent last-known-alive date).	
Tertiary/Exploratory		
Biomarker evaluation: To assess changes in tumor biomarkers.	Blood samples and biopsy samples will be collected to evaluate for biomarkers and changes in tumor microenvironment.	

4 STUDY DESIGN

4.1 OVERALL DESIGN

The study is designed as a prospective trial to evaluate the combination of cabozantinib and pembrolizumab in adult patients with advanced melanoma who did not previously receive cabozantinib. Prior use of anti-PD-1 inhibitors is allowed in the adjuvant setting provided that the last dose is longer than 6 months prior to developing metastatic disease. Pembrolizumab will be used at the recommended approved dose for this indication.

This single institution, investigator-initiated trial has two phases: a phase 1b dose escalation of cabozantinib in combination with pembrolizumab, to establish the recommended phase 2 dose for the combination. The Dose Escalation Phase will utilize a 3+3 design over 3 planned dose levels leading to the identification of aR2PD and MTD for the combination of cabozantinib and pembrolizumab.

This will be followed by a single-arm, open label, phase 2 study testing a fixed dose of cabozantinib combined with the standard-dose immune checkpoint inhibitor pembrolizumab. The study is powered to a primary endpoint of best ORR with the combination of cabozantinib and pembrolizumab. Secondary endpoints include clinical benefit (DCR and duration of DCR), time to response, PFS, and OS. Enrollment for Part 2 will commence only after a RP2D is identified from phase 1.

Treatment will be administered on an outpatient basis. Cabozantinib will be administered orally daily, and pembrolizumab will be intravenous infusion once every 3 weeks. Reported adverse events and potential risks are described in section 2.3. Appropriate dose modifications are described in Section 6.1.2.3. No investigational or commercial cancer directed agents or therapies other than those described below may be administered.

Safety assessment will follow the guidelines provided in the National Cancer Institute Common Terminology Criteria for Adverse Events (NCI-CTCAE) Version 4.03.

Subjects will be followed clinically on the D1 of each cycle and radio-graphically starting 12 weeks after initiation of treatment then every 12 weeks for tumor evaluation. Post-treatment scans will be compared to the baseline scan and responses will be assessed based using RECIST v1.1. Appendix A.

4.2 SCIENTIFIC RATIONALE FOR STUDY DESIGN

4.2.1 PHASE 1:

“Combination” clinical trials of novel immunological/targeted therapeutic agents assess the safety and/or efficacy of a combination of immunotherapeutic agents. While this begins to address understanding the potential benefit of such combinations seen in pre-clinical models, it complicates the assessment of the safety and efficacy of the immunologic agents. Phase 1 dose-escalation trials are especially difficult, since subjects are generally treated at the MTD of the backbone immunologic therapy, which, by definition, already induces significant toxicity in approximately 1/6 of subjects (the target rate of the 3 + 3 dose-escalation trial

design). The phase 1b dose escalation trial of combination immunotherapy that addresses these issues by escalating against the effect of regimen-limiting toxicity (RLT), i.e., toxicity induced by the immunological agents in combination that is not seen with either agent alone (or seen at severities or rates of occurrence above expected from existing data) is a reasonable approach. Additionally, if one of the agents is already approved and considered a standard of care regimen for the indication being studied, additional toxicities (as for type, severity or timing) seen above those expected that limit the administration of the backbone therapy could also be considered an RLT.

Cohorts of 3 to 6 subjects will be enrolled at each dose level and each subject will participate in only 1 cohort. The starting dose level (dose level 0) will be cabozantinib 40 mg daily, and pembrolizumab 200 mg once every 3 weeks as per the package label. The first subjects at each dose level will be treated and observed for DLT through the DLT assessment period (Study Day 1-21). If there is no DLT observed (Section 4.3.2) in the group of 3 or more subjects, the next cohort will be enrolled, and escalation will proceed to the next dose (dose level 1) cabozantinib 60 mg daily and pembrolizumab 200 mg once every 3 weeks as per the package label.

If a DLT is observed in 1 subject in the first 3 subjects enrolled in a cohort, enrollment will proceed, and the cohort size will be increased up to 6 subjects. If only 1 DLT is observed in 6 subjects in a cohort, escalation will proceed, and the next cohort may begin enrollment.

A minimum of 3 subjects will be enrolled in each Cohort. The maximum allowed DLTs per cohort to allow subsequent dose escalation is 1 DLT observed in 6 subjects. The sponsor may also choose to enroll up to 6 subjects initially into a cohort. Dose escalation will proceed if no more than 1 DLT is observed in 6 subjects to the next dose level. The dose level 1 will be the maximum allowed dose.

If ≥ 2 of 6 subjects experience a DLT in any cohort, dose escalation will cease and the previous lower dose of cabozantinib may be designated the MTD and RP2D. If ≥ 2 of 6 patients experience a DLT in the Dose level 0, then a step cohort (Dose level -1) will be enrolled with cabozantinib administered daily at 20 mg daily and pembrolizumab 200 mg once every 3 weeks, as per the package label. However, the sponsor may also decide to investigate an additional lower or intermediate dose group(s) than have already been tested. In such a scenario, the protocol will be amended. Subjects will be enrolled and evaluated as described above for previous dose escalation cohorts except that staggered enrollment with a sentinel subject will not be required. Three to 6 subjects will be enrolled at the intermediate or lower dose and DLT assessments performed, with expansion to 6 subjects as required and applicable. A maximum of 0 DLTs in the first 3 subjects or 1 DLT in the first 6 subjects will define this dose as the MTD.

4.2.2 PHASE 2:

The phase 2 part of the study will be run in two stages. In the first stage, 14 subjects will be accrued. If there are 5 or fewer responses in these 14 subjects, the study will be stopped.

Otherwise, 30 additional subjects will be accrued for a total of 44 subjects. This study design will have a limited enrollment of subjects to the trial if the combination does not show a

signal of activity in advanced melanoma.

4.2.3 BLINDING:

Blinding will not be performed as this is an open-label trial.

4.3 JUSTIFICATION FOR DOSE

4.3.1 PHASE 1B:

The Dose Escalation Phase 1b part will utilize a "3+3" design for escalation. The study plan includes the evaluation of 3 planned dose levels of cabozantinib administered orally. A minimum of 6 and a maximum of 18 subjects will be enrolled in each dose escalation cohort in Phase 1b, starting at 40 mg daily. The Sponsor reserves the right to adjust the planned cabozantinib dose levels based on emerging study data (Note: This will be considered as a protocol amendment) The planned cabozantinib dose levels to be studied in the Dose Escalation Phase 1b are presented in table 1. If the MTD has not been identified at the highest planned dose level, the Sponsor reserves the right to consider additional dose levels, and this would require a protocol amendment.

Table 1: Planned Dose Levels of Cabozantinib and Pembrolizumab

Dose Level	Cabozantinib	Pembrolizumab
-1	20 mg	200 mg
0 (starting dose)	40 mg	200 mg
1	60 mg	200 mg

Pembrolizumab will be administered at a standard recommended (drug label) dosing of 200 mg intravenously once every 3 weeks.

DLTs are defined in Section 4.3.2 Part 1 Dose Escalation: Dose-Limiting Toxicities (DLTs). The DLT rate across all subjects enrolled within a cohort in phase 1 must be <33% to allow escalation to the next dose level in that Arm. *The DLT observation period is 21 DAYS from date of first dose of cabozantinib.*

At the start of any new cohort, there will be a waiting period of at least 1 week after the first dose of the 3rd subject before enrollment of additional subjects into the same cohort. If a subject withdraws from the study prior to completion of the DLT assessment period for a reason other than a DLT, a replacement subject will be enrolled in that cohort.

Dose escalation in Part 1 to the next dose level can only occur after a minimum of 3 subjects have completed their DLT observation period for the current dose level, and the DLT rate does not exceed 33%.

Prior to escalation to a new dose level, the Safety Review Committee (SRC) will meet to review the safety data from the current cohort in order to determine if dose escalation is warranted.

The following rules govern dose escalation in Phase 1b:

- If none of the initial 3 subjects at a dose level experiences a DLT, escalation to the next dose level may occur. However, the Sponsor reserves the right to enroll up to 12 subjects in a cohort in order to obtain additional safety information.
- If 1 of the 3 initial subjects experiences a DLT, then 3 additional subjects will be enrolled in the same cohort (i.e., same dose level). If the DLT rate does not exceed 33% in the first 6 subjects, escalation to the next dose level may occur. However, the Sponsor reserves the right to enroll up to 12 subjects in a cohort in order to obtain additional safety information.
- If 2 or more subjects experience DLTs at a dose level, no further dose escalations will occur at that dose schedule. One or more lower dose level(s) may be tested in search of the MTD, defined as the dose level immediately below that in which ≥ 2 of 6 subjects experience DLTs.

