1.2 SCHEMA

Phase 1b:

Dose Level	Cabozantinib	Pembrolizumab
-1	20 mg	200 mg
0	40 mg	200 mg
1	60 mg	200 mg

Study Design

Phase 2: The target population includes patients with pathologic or cytologic evidence of melanoma, clinical stage IV or recurrent/medically inoperable disease, a ECOG performance score ≤ 2 and a life expectancy of >12 weeks, adequate hematologic, renal, and hepatic function, and measurable disease.

Patients who are taking other investigational agents, or who have uncontrolled CNS metastases or unstable medical conditions such as decompensated heart failure, unstable angina, uncontrolled hypertension or diabetes and active infections are to be excluded from this study. Treatment will begin only after patients have fully met all inclusion criteria and none of the exclusion criteria and a valid informed consent has been signed.

Subjects will receive cabozantinib, orally at the MTD dose obtained from phase 1b part of the study in combination with pembrolizumab administered IV at 200 mg once every 3 weeks. After baseline tumor evaluation, tumor assessments will be performed with interval imaging every 12 weeks starting from Week 12 until progression with a CT scan and response evaluated per RECIST 1.1. Appendix A. Progressive disease per RECIST or unacceptable toxicity will result in the subject's termination of the study drug.

Prognostic Stage Group: the eighth edition American Joint Committee on Cancer (AJCC) melanoma staging system groups patients into four prognostic stage groups. The details of prognostic group staging:

- Stage I – Stage I melanoma is limited to patients with low-risk primary melanomas (T1a, T1b, and T2a) without evidence of regional or distant metastases. Stage I is divided into stages IA and IB based upon the thickness of the primary tumor and the presence or absence of ulceration.
- Stage II – Stage II disease includes primary tumors that are at higher risk of recurrence (T2b, T3a, T3b, T4a, and T4b) but do not have any evidence of lymphatic disease or distant metastases. Stage II is divided into stage IIA, IIB, and IIC depending upon tumor thickness and the presence or absence of ulceration.
- Stage III – Stage III disease includes pathologically documented involvement of regional lymph nodes or the presence of in transit or satellite metastases (N1, N2, and N3). Patients with stage III disease are subclassified as having stage IIIA, IIIB, IIIC, or IIID disease depending upon the extent of lymphatic disease.

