9.2 SAMPLE SIZE DETERMINATION

Phase 1:

Phase I will utilize a standard 3+3 dose escalation design. A minimum of 6 and a maximum of 18 evaluable patients are required.

Phase 2:

When testing the null hypothesis that the $\text{ORR} \leq 35\%$ versus the alternative hypothesis that the $\text{ORR} \geq 55\%$, a sample size of 44 evaluable patients will ensure 80% power to detect a 20% absolute increase in ORR using an optimal Simon's two-stage design (Simon, 1989). Power estimates are based on an alpha = 0.05.

Based on historical trends our institution, the anticipated accrual rate is 2-3 patients per month.

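### Section 4.3.1 gives the Phase 1 total of 6 to 18 as the size of each cohort, and the escalation rules do not require the six patients that 9.4.2 names at the Phase 2 dose

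*Combined protocol and SAP*

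**What the plan says.** On the size of Phase 1b:

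- Section 4.3.1: "A minimum of 6 and a maximum of 18 subjects will be enrolled in each dose escalation cohort in Phase 1b".
- Section 9.2, for Phase 1 as a whole: "A minimum of 6 and a maximum of 18 evaluable patients are required".
- Section 4.2.1: "Cohorts of 3 to 6 subjects will be enrolled at each dose level and each subject will participate in only 1 cohort".
- The escalation rules in 4.3.1 work on three subjects, then six, and add that "the Sponsor reserves the right to enroll up to 12 subjects in a cohort in order to obtain additional safety information".

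On choosing the dose:

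- Section 4.3.1: "If none of the initial 3 subjects at a dose level experiences a DLT, escalation to the next dose level may occur". Section 4.2.1 has the same rule.
- Section 4.2.1, when two or more of six subjects in a cohort have a DLT: "dose escalation will cease and the previous lower dose of cabozantinib may be designated the MTD and RP2D".
- Section 4.2.1 makes 60 mg the highest allowed dose. Neither section requires 60 mg to be filled to six after 0/3.
- Section 4.2.1, at the end of its text on a lower or intermediate dose: "A maximum of 0 DLTs in the first 3 subjects or 1 DLT in the first 6 subjects will define this dose" as the MTD. An additional dose group needs a protocol amendment, but the sentence can also be read to cover the planned 20 mg level.
- Section 1.2: "Subjects will receive cabozantinib, orally at the MTD dose obtained from phase 1b part of the study".
- Section 9.4.2 defines the recommended Phase 2 dose (RP2D) as the highest level at which no more than one of six patients has a DLT.

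**The concern.** There are two separate problems. First, the cohort size in 4.3.1 contradicts 9.2, 4.2.1 and the rules in its own section, and the 12-subject option does not fit under the 9.2 maximum. Second, two standards apply to the dose that goes forward. The escalation text can be satisfied with three patients at that dose, while the statistical section names six.

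Phase 1b sets the cabozantinib dose for up to 44 Phase 2 patients. A reader cannot tell from the text whether three or six DLT-evaluable patients are needed at that dose.

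**Working it through.** **Inputs.** Three planned levels (20, 40 and 60 mg, starting at 40 mg) and the escalation rules come from 4.2.1 and 4.3.1. The total of 6 to 18 comes from 9.2, and the RP2D rule from 9.4.2. The documents give no true DLT rate, so the rates in step 5 are assumptions.

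**1. The plan's own figure.** Two levels × 3 = 6 and three levels × 6 = 18. The 9.2 range is reproduced as a Phase 1 total.

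**2. The 4.3.1 wording taken literally.** With 6 to 18 per cohort, two levels would need 12 to 36 patients (2 × 6 to 2 × 18) and three levels 18 to 54 (3 × 6 to 3 × 18). Neither range matches 9.2. A minimum of six per cohort also contradicts escalation after 0/3 in the same section.

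**3. The 12-subject option.** 2 × 12 = 24 and 3 × 12 = 36. Both exceed 18.

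**4. Routes to a Phase 2 dose resting on three patients.**

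- 40 mg clears on 0/3, 60 mg fails, and 40 mg may be named MTD and RP2D.
- 60 mg clears on 0/3. It is the top dose, and no expansion is required.
- 40 mg fails, 20 mg shows 0/3, and the 0-in-3 sentence is read to cover that level.

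Each route meets the escalation text. None meets 9.4.2 read literally.

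**5. What three patients show.** The exact one-sided 95% upper limit on the DLT rate, which needs no assumed rate, is:

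| Result | Calculation | Upper limit |
|---|---|---|
| 0/3 | 1 − 0.05^(1/3) | 63% |
| 0/6 | 1 − 0.05^(1/6) | 39% |
| 1/6 | p solving (1−p)^6 + 6p(1−p)^5 = 0.05 | 58% |

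After 0/3, the dose fails the six-patient rule if at least two of the next three patients have a DLT. That probability is 3p²(1−p) + p³:

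| Assumed true DLT rate p | Calculation | Probability of failing |
|---|---|---|
| 10% | 0.027 + 0.001 | 0.028 |
| 20% | 0.096 + 0.008 | 0.104 |
| 30% | 0.189 + 0.027 | 0.216 |

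**6. Totals if six are required at the chosen dose.** When a second level is opened and an RP2D is named, the smallest total is 3 + 6 = 9. Examples are three at 40 mg and six at 60 mg, or three at a failed 40 mg and six at 20 mg. The largest, without the 12-subject option, stays at 18: 40 mg clears on 0/3, 60 mg fails in six, 40 mg is filled to six and fails, and 20 mg takes six.

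**The case against.** **The statistical section already supplies the six-patient rule.** Sections 4.1 and 4.3.3 require an RP2D before Phase 2, and 9.4.2 defines it. The 0-in-3 sentence defines an MTD, and the text on naming the dose below a failed one is permissive. If 9.4.2 controls, 40 mg and 60 mg are settled. This stands in part. But no section says that 9.4.2 controls, 4.2.1 lets one dose be both MTD and RP2D, and 1.2 gives Phase 2 patients the MTD.

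**The 0-in-3 sentence is conditional.** An additional lower or intermediate dose needs an amendment, which could restate the rule. That is fair for an added level. It does not remove the ambiguity for 20 mg, which is already planned.

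**One in six may be a rate ceiling.** On that reading 0/3 also passes and the two standards agree. The literal text names six patients, but the reading is possible, so the protocol should say which is meant.

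**The effect is small.** The upper limit after 0/3 is only 5 points above that after 1/6 (63% against 58%), and 9.4.2 accepts 1/6. This is correct and limits the weight of the point. The more direct comparison for a dose with no DLTs is 63% against 39%.

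**The cohort-size error is editorial.** The detailed rules make it unlikely that anyone would enrol 18 in a cohort. Agreed, but the sentence is still a wrong statement of sample size.

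**Conclusion.** The point holds as an error in stated cohort size and an unresolved difference between two dose-selection rules. The first part rests on the text alone. The second rests on reading 9.4.2 literally. Its practical size is modest: a 3% to 22% chance that a dose cleared on 0/3 would fail if filled to six, at assumed DLT rates of 10% to 30%.

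Three stronger readings are not supported:

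- A reader might infer that the Phase 2 dose will rest on three patients. The text permits this but does not require it; the sponsor may start a cohort with six or enlarge it.
- A reader might infer from the maximum of 18 that 9.2 presupposes six patients at the chosen dose. It does not settle the matter. Section 4.3.1 allows lower levels to be tested after a failure, so a third level can open in any case. The minimum of 6 can be reached by 0/3 at 40 mg and then 0/3 at 60 mg.
- A reader might take this as a criticism of escalating on 0/3. That is ordinary 3+3 practice; the gap concerns naming the Phase 2 dose.

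**What to change.** - **4.3.1:** state 6 to 18 as the Phase 1 total, with 3 to 6 per cohort.
- **9.2:** keep the 12-subject option, which serves safety, but restate the maximum to allow for it (24 over two levels, 36 over three). Note that at least 9 patients are needed when a second level is opened and an RP2D is named.
- **4.2.1, 4.3.1 and 9.4.2:** state that the RP2D needs at most one DLT in six DLT-evaluable patients, and that any dose cleared on 0/3, including 60 mg and 20 mg, is filled to six before it is named. If a rate ceiling was intended instead, say so explicitly.
- **4.2.1:** amend the 0-in-3 MTD sentence to match.

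The cost is the rewording plus up to three more patients at the chosen dose. If Phase 1b is already complete, report the number of DLT-evaluable patients and of DLTs at the chosen dose.
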